## 2 Study Rationale

As often occurs, clinical practice has moved beyond what has been demonstrated in clinical trials. To date, no studies have evaluated the safety and impact of treatment with multiple approved aesthetic products. The objective of the initial HARMONY USA study was to observe overall aesthetic impact of treating subjects with several modalities in an attempt to achieve subjects' desired clinical outcome. The HARMONY Brazil study will expand upon the products tested, the facial areas treated, and the quantification of the psychological and emotional impact of the comprehensive aesthetic treatment provided and will ultimately be global in scope.

In the HARMONY Brazil study, subjects will be evaluated by the investigator to receive BOTOX, HArmonyCa Lidocaine facial filler, and Juvéderm facial fillers (JUVÉDERM VOLITE [REDACTED], JUVÉDERM VOLBELLA with Lidocaine, JUVÉDERM VOLIFT with Lidocaine, JUVÉDERM VOLUMA with Lidocaine, and JUVÉDERM VOLUX with Lidocaine). Selected subjects will receive staged treatment with the multiple products and will be evaluated using validated patient-reported outcome measurements to determine the psychological and emotional impact of an integrated treatment approach to reduce visible signs of aging.

The clinical hypothesis of this study is that subjects treated with a combination of BOTOX, HarmonyCa Lidocaine facial filler, and JUVÉDERM facial fillers will be satisfied with their overall facial appearance at the final study visit as measured by the change from baseline on the FACE-Q Satisfaction with Facial Appearance Overall Scale.

### 3 Study Objectives

#### 3.1 Primary Objective

The primary objective of this study is to quantify the psychological, social, and emotional impact of comprehensive aesthetic treatment with a portfolio of the Sponsor's products by measuring the change in subject's satisfaction with facial appearance from baseline (before any treatment) to the final study visit ([Appendix 4](#) FACE-Q™: Satisfaction with Facial Appearance). These products include BOTOX, HArmonyCa Lidocaine, and Juvéderm HA facial fillers, as described in Section [9](#).

#### 3.2 Secondary Objectives

Secondary objectives are:

- To determine the subject's self-appraisal of age-related facial appearance ([Appendix 4](#) FACE-Q®: Aging Appraisal), psychological function ([Appendix 5](#) FACE-Q™: Psychological Function), social function ([Appendix 6](#) FACE-Q™: Social Function) and overall satisfaction with skin ([Appendix 7](#) FACE-Q™ Satisfaction with Skin Questionnaire).
- To quantify the investigator's and subject's assessment of aesthetic improvement.

## 4 Study Design

### 4.1 Study Design Overview

This Phase 4 study is a prospective, interventional, multicenter, combination medical device and drug post marketing study. Each subject will be in the study for up to approximately 5 months and act as his/her own control. All products will be used as per their license only. The investigators will perform all treatments and evaluations.

[figure not shown]
The study is planned to enroll 60 subjects consecutively at approximately 7 study sites in Brazil. Recruitment will also target men, who are typically under-represented in aesthetic studies.

Detailed descriptions of all study procedures by study visit and study treatment are presented in [Table 6.1](#) and [Section 6](#).

All subjects will sign an informed consent form (ICF) and begin at the screening visit (V0). Subjects will enter the study at V1 to begin treatment with facial fillers and will receive BOTOX starting at V3, as indicated in the study design diagram ([Figure 4.1](#)). In order to reduce the number of subject visits, Visit 0 can be combined with the initial treatment visit, if judged by the investigator to be appropriate and acceptable for the subject. Identical study procedures will not be repeated where the visits are combined.

**Figure 4.1**

**Overall Study Design**

## 4.2 Study Endpoints

### 4.2.1 Primary Endpoint

The primary endpoint is the change from before any treatment (baseline, V0) in the Rasch-transformed score of the FACE-Q Satisfaction with Facial Appearance Overall Scale to the final study visit (V7).

### 4.2.2 Key Secondary Endpoints

#### 4.2.2.1 FACE-Q Questionnaires

- Subject's assessment of age-related facial appearance as measured by the change from baseline before any treatment in the Rasch-transformed score of the FACE-Q Aging Appraisal to final study visit (V7)
- Subject's assessment of psychological well-being as measured by the change from baseline before any treatment in the Rasch-transformed score the FACE-Q Psychological Function Scale to final study visit (V7)
- Subject's assessment of social function as measured by the change from baseline before any treatment in the Rasch-transformed score of the FACE-Q Social Function scale to final study visit (V7)
- Subject's assessment of overall satisfaction with skin as measured by the change from baseline before any treatment in the Rasch-transformed score of the FACE-Q Satisfaction with Skin to final study visit (V7)

#### 4.2.2.2 Self-Perception of Age Questionnaire

Subject's assessment of age-related facial appearance by the self-perception of age (SPA) measure at baseline before any treatment to final study visit (V7); responders are defined as having achieved a younger category.

### 4.2.3 Other Secondary Endpoints

#### 4.2.3.1 Global Aesthetic Improvement Scale

- Investigator's assessment of global facial aesthetic improvement as measured by the 5-point global aesthetic improvement scale (GAIS) at final study visit (V7).
- Subject's assessment of global facial aesthetic improvement as measured by the 5-point GAIS at final study visit (V7).

#### 4.2.3.2 Periorbital Aesthetic Appearance Questionnaire

- Change in subject's satisfaction with appearance of periorbital area as measured by the periorbital aesthetic appearance questionnaire (PAAQ) from baseline to final study visit (V7).

### 4.3 Safety

All adverse events (AEs) including injection site reactions (ISRs) will be collected from when the ICF is signed through to the last study visit (V7). Serious adverse events (SAEs) will be reported within the specified time and format directly to the Sponsor as described in Section 10.5.

### 4.4 Blinding and Randomization

Blinding and randomization are not applicable. This is an open-label, single-arm study. Subjects are enrolled consecutively based upon subject need and all subjects are intended to receive all treatments. Investigators will perform all treatments and evaluations.

## 5 Selection of Subjects

Approximately 60 subjects will be enrolled at approximately 7 sites in Brazil. Subjects will be assigned to study treatment only if they meet all of the inclusion criteria and none of the exclusion criteria. Subjects who discontinue treatment will not be replaced.

### 5.1 Inclusion Criteria

The following are requirements for entry into the study.

1. 35 to 65 years of age, inclusive, at screening (male or female)
2. Accept the obligation not to receive any other facial procedures or treatments at any time during the study that are not related to the study
3. Women of childbearing potential must have a negative urine pregnancy test before each injectable treatment and practice a reliable method of contraception throughout the study
4. Willing to avoid direct and prolonged sun exposure to the facial skin, which includes tanning beds, for the duration of the study
5. Must qualify to receive BOTOX treatments, in at least one area, as per the approved Product Monograph including treatment of hyperkinetic lines for the glabellar, crow's feet, and forehead lines:
  - Glabellar injection: glabellar rhytides characterized as 2 (moderate) or 3 (severe) during maximum muscle contraction on the evaluation of the facial wrinkle scale (FWS)
  - CFLs characterized as 2 (moderate) or 3 (severe) during maximum smile on the evaluation of the FWS
  - FHLs of 2 (moderate) to 3 (severe) rating at maximum eyebrow elevation as assessed using the FWS
6. Must qualify to receive Juvéderm dermal filler treatments as per the approved Directions for Use. Subjects must use at least two different Juvéderm filler products in at least two different aesthetic anatomic areas. A summary of inclusion criteria by facial area for potential subjects for filler treatments is presented in [Table 5.1](#).

**Table 5.1 Summary of Inclusion Criteria by Facial Area for Potential Subjects for Filler Treatments**

Product	Indication	Contra-indications
JUVÉDERM VOLBELLA with Lidocaine	Treatment of any fine lines and medium-sized skin depressions. Can also be used for enhancement and pouting of the lips to correct structural defects such as asymmetry, contour deformities, volume loss.	
 
Do not inject into the eyelids. The application in the bags under the eyes is reserved to specialists specifically trained in this technique and having a sound knowledge of the physiology for this particular area.
 
Do not inject into the blood vessels (intravascular). Intravascular injection may lead to embolization, occlusion of the vessels, ischemia, or infarction.
 
Do not overcorrect.
 

JUVÉDERM VOLIFT with Lidocaine	Intended for the treatment of any deep skin depressions due to conditions such as premature aging. Can also be used for face contouring and volume restoration to correct facial structural defects such as asymmetry, contour deformities, volume loss in the lips, cheeks, chin, lower face.	
 
Do not inject in the periorbital area (eyelids, under-eye area, crow's feet) and glabellar region.
 
Do not inject into the blood vessels (intravascular). Intravascular injection may lead to embolization, occlusion of the vessels, ischemia, or infarction.
 
Do not overcorrect.
 

JUVÉDERM VOLUMA with Lidocaine	Intended to restore volume of the face	
 
Do not inject in the periorbital area (eyelid, under-eye area, crow's feet), in the glabellar region or in the lips.
 
Do not inject into the blood vessels (intravascular). Intravascular injection may lead to embolization, occlusion of the vessels, ischemia, or infarction.
 
Do not overcorrect.
 

JUVÉDERM VOLITE [REDACTED]	Intended for treatment, by filling, of superficial cutaneous depressions such as fine lines and for additional improvement of skin quality attributes such as hydration and elasticity.	
 
Do not inject in the eyelids.
 
Do not inject into the blood vessels (intravascular). Intravascular injection may lead to embolization, occlusion of the vessels, ischemia, or infarction.
 
Do not overcorrect.
 

JUVÉDERM VOLUX with Lidocaine	Intended to restore and generate facial volume in chin and mandible areas	
 
Do not inject in the periorbital area (eyelid, under-eye area, crow's feet), in the glabellar region or in the lips.
 
Do not inject into the blood vessels (intravascular). Intravascular injection may lead to embolization, occlusion of the vessels, ischemia or infarction.
 
Do not overcorrect
 

HArmonyCa Lidocaine	Intended for facial soft tissue augmentation.	
HArmonyCa Lidocaine is contraindicated:
 
 
in patients with a known sensitivity to any of the product components.
 
in patients suffering from skin disease or abnormal skin conditions.
 
in patients suffering from an infection or inflammation (either acute or chronic) at or near the treatment site.
 
in patients susceptible to keloid formation, hypertrophic scarring, or developing inflammatory skin conditions.
 

Product	Indication	Contra-indications
		
 
• in patients with impaired wound healing due to systemic disorders, medicinal drugs, or unhealthy or poorly-vascularized tissue.
 
• in patients suffering from prolonged bleeding or tissue healing due to medical conditions or medicinal drugs.
 
• in patients with a history of anaphylactic reactions and/or multiple severe allergies.
 
• in patients with a known sensitivity to steroids, or who are contraindicated to be treated with steroids.
 
• for injection into the glabellar or periocular areas.
 
• for injection into the lips and perioral region.
 
• for injection into regions containing foreign bodies.
 
• in patients presenting with herpes.
 
• in patients with autoimmune diseases.
 
• for injection into blood vessels and to highly vascularized areas.
 
• for injection into the epidermis or superficial dermis.
 
• in breastfeeding or pregnant women.
 
• in patients below the age of 18.
 

**The investigator should not inject greater than 20 mL of filler (Juvéderm and HArmonyCa) per 60 kg (130 lbs.) body mass per year for a single subject.**

## 5.2 Exclusion Criteria

The following criteria exclude potential subjects from participating in the study:

1. Body mass index (BMI) > 30 kg/m^2
2. Known allergy or sensitivity to the study products or their components
3. Pregnant, lactating, or planning to become pregnant at any time during the study
4. Received BOTOX or treatment with any other botulinum toxin product for any condition within 6 months before enrollment
5. Received (or is planning to receive) anticoagulation, antiplatelet or thrombolytic medications (e.g., warfarin) or other substances known to increase coagulation time from 10 days prior to injection and up to 3 days post-injection
6. Undergone plastic surgery of the face and/or neck, tissue grafting, or tissue augmentation with silicone, fat, or other permanent dermal fillers, or be planning to undergo any of these procedures at any time during the study
7. Has undergone temporary or semi-permanent facial or neck dermal filler treatment (e.g., hyaluronic acid, calcium hydroxylapatite, poly-L-lactic acid) within 12 months before enrollment
8. Received mesotherapy, skin resurfacing (laser, photomodulation, intense pulsed light, radio frequency, dermabrasion, chemical peel, or non-ablative procedures) in the face or neck within 6 months prior to study enrollment

9. Marked facial asymmetry, brow or eyelid ptosis, excessive dermatochalasis, deep dermal scarring, thick sebaceous skin, or an inability to substantially lessen the resting GLs and CFLs/facial rhytides by physically spreading them apart
10. Lip tattoos, facial hair or scars that would interfere with visualization of the lips and perioral area for the effectiveness assessments
11. At any proposed injection site, presence of inflammation, infection at any injection site or systemic infection (study entry may be postponed until one week following recovery), noticeable acne scarring, cancerous or pre-cancerous lesion, or unhealed wound or have undergone radiation treatment in the area to be treated
12. Received any investigational product within 60 days prior to study enrollment or planning to participate in another investigation during the course of this study
13. An employee (or a relative of an employee) of the investigators, the Sponsor, or representative of the Sponsor
14. Condition or in a situation that, in the investigator's opinion, may put the subject at significant risk, may confound the study results, or may interfere significantly with the subject's participation in the study
15. Current use of oral corticosteroids
16. Current use of nonsteroidal anti-inflammatory drugs (NSAIDs) (e.g., aspirin, ibuprofen), from 10 days prior to injection up to 3 days post-injection
17. Prescription topical retinoid therapy and/or topical hormone cream applied to the face, for potential subjects who have not been on a consistent dose regimen for at least 6 months prior to enrollment and who are unable to maintain regimen for the study
18. Systemic retinoid therapy within one year prior to study enrollment
19. History or current symptoms of dysphagia
20. Medical condition that may increase the risk of exposure to botulinum toxin including diagnosed myasthenia gravis, Eaton-Lambert Syndrome, amyotrophic lateral sclerosis, or any other disease that might interfere with neuromuscular function
21. Current use of aminoglycoside antibiotics, curare-like agents, or agents that might interfere with neuromuscular (skeletal) function
22. Profound atrophy/excessive weakness of muscles in target areas of injection
23. History of facial nerve palsy
24. Anticipated need for treatment with botulinum toxin of any serotype for any reason during the study (other than study treatment)
25. Very thin skin in the mid-facial region
26. Tendency to accumulate fluid in the lower eyelids, or large infraorbital fat pads, i.e., significant convexity or projection from the infraorbital fat pads
27. Mid-face volume deficit due to congenital defect, trauma, abnormalities in adipose tissue related to immune-mediated diseases such as generalized lipodystrophy (e.g., juvenile dermatomyositis), partial lipodystrophy (e.g., Barraquer-Simons syndrome), inherited disease, or human immunodeficiency virus-related disease

28. Undergone oral surgery or other dental procedures (e.g., tooth extraction, orthodontia, or implantation) within 30 days prior to enrollment or be planning to undergo any of these procedures during the study
29. Subjects with neuromuscular disorders including generalized muscle weakness, diplopia, ptosis, dysphonia, dysarthria, severe dysphagia, and respiratory compromise
30. Subjects with a history of allergies or hypersensitivity to hyaluronic acid or lidocaine

### 5.3 Summary of Required Washout Periods

Potential study subjects may have used the following products and procedures (Table 5.2) that have specified washout periods prior to baseline visits for all subjects.

**Table 5.2 Products and Procedures with Washout Periods Taken by Potential Subjects Prior to Study Enrollment**

Product or Procedure	Washout Prior to Baseline

 
• Anticoagulation, antiplatelet or thrombolytic medications (e.g., warfarin) or other substances known to increase coagulation time
 
• NSAIDs (e.g., aspirin, ibuprofen) 
 
	10 days, and to 3 days post injection
• Systemic retinoids	1 year
• Prescription topical retinoid and/or hormone cream (if not a consistent dose regimen)	6 months

 
• Current use of aminoglycoside antibiotics, curare-like agents, or agents that might interfere with neuromuscular (skeletal) function
 
• Systemic corticosteroids
 
• Oral surgery or other dental procedures
 
	30 days
• Received any other investigational product	60 days

 
• Mesotherapy or Skin resurfacing (e.g., laser, photomodulation, intense pulsed light, radio frequency, dermabrasion, chemical peel, or non-ablative procedures) in the face or neck
 
• History of ocular surgery
 
	6 months
• BOTOX or any other botulinum toxin product	6 months
• Temporary or semi-permanent facial or neck dermal filler treatment (e.g., hyaluronic acid, calcium hydroxylapatite, poly-L-lactic acid)	12 months

Abbreviations: NSAIDs = non-steroidal anti-inflammatory drugs

 For subjects being treated for cardiac conditions with aspirin and/or anti-coagulants, approval from a cardiologist is required prior to enrollment in the study.

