## 5.4 Other Restrictions and Precautions

### 5.4.1 Prohibited Medications and/or Treatments

Subjects must not undergo any type of facial plastic or reconstructive surgery or cosmetic procedure (e.g., plastic surgery; tissue grafting; tissue augmentation with silicone, fat, or other permanent, semi-permanent, or temporary dermal fillers; neuromodulator injections; or mesotherapy; or ablative procedures) at any time during this study.

The decision to administer a prohibited medication/treatment will be made with the safety of the study participant as the primary consideration. When possible, the Sponsor or the Sponsor's representative should be notified before a prohibited medication/treatment is administered. Prior to attending study visits, subjects must not apply facial cosmetics.

Therapy considered necessary for the subject's welfare may be given at the discretion of the investigator, including but not limited to medications for other conditions (i.e., hypertension, diabetes, etc.), treatment of AEs, estrogens, androgens, anti-androgenic agents, vitamins, iron supplements, folate, and herbal supplements. Medications should be taken consistently throughout the study and at the investigator's discretion.

Concomitant medications as defined for this study include dietary supplements, over-the counter medications, and oral herbal preparations, as well as changes in dosages of current prescription medications. Concomitant medications will be documented for each subject at each scheduled visit. A detailed history of medications will be documented at screening. Subsequently, at each study visit, subjects will be asked what medication, if any, they have taken since the previous visit. All concomitant medications will be recorded on electronic case report forms (eCRFs).

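### Footnote 1 of Table 5.2 does not fit exclusions 5 and 16: cardiac subjects on aspirin or anticoagulants may enter with a cardiologist's approval, but the protocol does not say whether the drug is continued or stopped

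*Protocol*

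**What the plan says.** Section 5 admits subjects without exceptions: "Subjects will be assigned to study treatment only if they meet all of the inclusion criteria and none of the exclusion criteria". Two exclusions in Section 5.2 matter here, and the synopsis repeats both.

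- Exclusion 5: "Received (or is planning to receive) anticoagulation, antiplatelet or thrombolytic medications (e.g., warfarin) or other substances known to increase coagulation time", from 10 days before to 3 days after injection.
- Exclusion 16: "Current use of nonsteroidal anti-inflammatory drugs (NSAIDs) (e.g., aspirin, ibuprofen), from 10 days prior to injection up to 3 days post-injection".

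Neither has a cardiac exception. Table 5.2 lists the same drugs as items to wash out, with the period "10 days, and to 3 days post injection". Footnote 1 is attached to both entries. It says that for subjects "being treated for cardiac conditions with aspirin and/or anti-coagulants, approval from a cardiologist is required prior to enrollment".

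Three other passages bear on how the footnote is read. Section 5.4.1 allows therapy needed for the subject's welfare and asks for medication to be taken consistently, at the investigator's discretion. Table 5.1 contraindicates HArmonyCa "in patients suffering from prolonged bleeding or tissue healing due to medical conditions or medicinal drugs". Exclusion 14 lets the investigator refuse anyone whose condition "may put the subject at significant risk".

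**The concern.** The footnote makes approval a condition of entry for people whom the exclusions would otherwise keep out while they take the drug. It does not say whether the cardiologist approves stopping the drug, continuing it, or simply taking part. Two sites could treat the same cardiac patient in opposite ways, and each could cite the protocol.

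This is a matter of subject safety. On one reading a subject is injected while taking a drug that the exclusions bar around injection. On the other, prescribed antithrombotic treatment is interrupted, perhaps several times, for elective cosmetic injections. No study objective needs such subjects.

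The footnote is also narrower than the exclusions. It covers cardiac conditions only, and aspirin or anticoagulants only. Exclusion 5 reaches any antiplatelet or thrombolytic drug for any indication. A subject on another antiplatelet, or on an anticoagulant for a non-cardiac reason, faces the same window with no specialist asked.

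**Working it through.** The protocol gives no number of interruptions or days off drug, so there is no stated figure to reproduce. The check takes each reading in turn.

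**Reading A: the drug is continued with approval.** Days off drug: 0. An anticoagulant taken within the window meets exclusion 5, and aspirin meets exclusion 16. Section 5 then bars study treatment. For HArmonyCa, the contraindication on prolonged bleeding due to medicinal drugs points the same way.

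**Reading B: the drug is stopped around injection.** The exclusions are respected, but this sits badly with the request in Section 5.4.1 for consistent medication.

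Length of one block: 10 days before + the injection day + 3 days after = 14 days.

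Number of sessions, from Table 6.1 and Sections 6.2.2 to 6.2.5: HArmonyCa (V1, V2) is optional, as are the touch-ups at V2, V5 (Juvéderm) and V6. BOTOX is given at V5. V4 is a mandatory visit whether or not more filler is expected, although Section 6.2.3 lists filler injection among its procedures. If the window applies to each injection, total days = sessions × 14:

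| Course | Sessions | Days off drug |
|---|---|---|
| No HArmonyCa; V3 activities and V5 only | 2 | 2 × 14 = 28 |
| No HArmonyCa; V3, V4, V5 | 3 | 3 × 14 = 42 |
| V1, V3, V4, V5, no touch-ups | 4 | 4 × 14 = 56 |
| V1 to V6 all injected | 6 | 6 × 14 = 84 |

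If V4 is always injected, the minimum is three sessions.

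**Do the blocks overlap?** Days back on drug between two blocks = spacing − 14.

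- Visits 30 ± 7 days apart: 23 − 14 = 9, up to 37 − 14 = 23.
- V5 to V6 (15 + 7 days): 15 − 14 = 1, up to 22 − 14 = 8.

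The blocks therefore stay separate throughout the protocol's windows, and the totals do not depend on visit timing. One copy of the SAP schedule header prints V6 as 15 ± 7 days. At a spacing of 8 days the last two blocks would overlap by 14 − 8 = 6 days and the maximum would be 84 − 6 = 78. The protocol and the other SAP header give 15 + 7.

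On the nominal six-session schedule (Day 1 to Day 135), the span from the start of the first block to the end of the last is (135 − 1) + 1 + 10 + 3 = 148 days, so 84/148 = 57% of it is off drug.

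**Reading C: the window applies only around the first injection.** The total is 14 days, but a subject who resumes the drug then meets exclusion 5 or 16 at later injections unless the word injection is read as the first one only.

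**Checks at the visits.** At each visit "subjects will be asked what medication, if any, they have taken since the previous visit". The filler steps for V1 to V4 refer to areas qualified for under the eligibility criteria. The V5 and V6 steps do not. No visit has an explicit check of the 10-day/3-day window before injecting.

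**The case against.** The strongest reply is that nothing in the protocol tells anyone to stop an antithrombotic. The exclusions bar users and do not order withdrawal. They refer to injection, not to each injection. Section 5.3 and the column heading of Table 5.2 speak of washout before baseline. The footnote describes people currently under treatment and is attached to exactly the two entries it qualifies, so it can be read as a cardiac exception: continue, with approval. Section 5.4.1 supports that. All of this stands, and it is why repeated interruption can only be given as a conditional figure. It does not remove the problem, because continuing still contradicts exclusions 5 and 16, and the post-injection half of the window has no meaning at baseline alone.

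There are also real safeguards. Exclusion 14 covers any drug and any indication. Section 6.2.1 has the status of washouts documented at screening. Section 8.2 lists meeting an exclusion criterion as a possible reason for discontinuation. Section 9.2 has monitors review eligibility. A cardiologist may refuse or set conditions, and nothing prevents a second consultation. These give partial protection, but none says which of the two courses to follow.

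A lighter remedy would be one sentence stating what is approved and for which injections. That would cure the ambiguity, but it would leave the sponsor choosing between waiving an exclusion and interrupting treatment.

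**Conclusion.** The footnote and the exclusions do not fit together, and the text should be corrected. Continuing the drug gives 0 days off drug and breaches exclusion 5 or 16. Stopping it gives 28 to 84 days in two to six blocks (at least three blocks, 42 days, if V4 is always injected). That range assumes that the window applies to every injection, BOTOX included, and that the protocol's visit windows hold.

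A reader might infer that the plan will repeatedly interrupt prescribed treatment. The documents do not support that: no passage orders it, and a site could equally continue the drug or decline to enrol the subject. Nor do they support a claim about the results. The number of such subjects is not given and may be zero, and nothing here changes the sample size or the primary analysis. The SAP removes a subject from the Evaluable Population only for significant violations or deviations that affect an efficacy endpoint.

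This is an avoidable safety ambiguity that is cheap to remove. It should be fixed, but it is not critical to the study's conclusions.

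**What to change.** Replace footnote 1, and add to exclusions 5 and 16 in Section 5.2 and in the synopsis:

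*Subjects taking prescribed or physician-directed long-term aspirin, antiplatelet or anticoagulant therapy for any medical indication are not eligible, and such therapy must not be stopped for the study.*

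Keep the 10-day/3-day window for occasional aspirin and other NSAID use. Confirm it before each injection at V1 to V6, where concomitant medications are already recorded. Limiting the rule to long-term, physician-directed therapy keeps an occasional aspirin for a headache under the window and not under the ban.

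The cost is a wording amendment, one confirmation at each injection visit and possibly a few more screen failures. Sample size and analysis are unchanged.
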